4.3.4. Physical Examination Findings

Abnormal physical examination will be listed.

4.3.5. Electrocardiogram

PR, QT, QRS, QTc intervals and heart rate will be investigated. QTc values will be used as reported, they will not be recalculated.

Definitions

The following abnormalities will be defined:

Abnormality Code	ECG parameter			
	HR	PR	QRS	QT _{corrected}
Abnormalities on actual values				
Abnormally low	< 45 bpm	< 110 ms	-	-
Abnormally high	≥ 120 bpm	> 220 ms	≥ 120 ms	-
Borderline prolonged QT (males)	-	-	-	$450 \text{ ms} < \text{QTc} \leq 480 \text{ ms}$
Borderline prolonged QT (females)	-	-	-	$470 \text{ ms} < \text{QTc} \leq 480 \text{ ms}$
Prolonged QT	-	-	-	$480 \text{ ms} < \text{QTc} \leq 500 \text{ ms}$
Pathologically prolonged QT	-	-	-	$\text{QTc} > 500 \text{ ms}$
Abnormalities on changes from baseline (ΔQTc)				
Normal QTc change	-	-	-	$\Delta\text{QTc} < 30 \text{ ms}$
Borderline QTc change	-	-	-	$30 \text{ ms} \leq \Delta\text{QTc} \leq 60 \text{ ms}$
Abnormally high QTc change	-	-	-	$\Delta\text{QTc} > 60 \text{ ms}$

In determining the abnormalities, the following rules are applied:

- worst grades/abnormalities are determined over the whole observational period for each trial phase separately, including post-baseline scheduled and unscheduled measurements of that phase.
- The abnormalities ‘abnormally low’ and ‘abnormally high’/grades are considered equally important, i.e. if a subject has as well an abnormally low as an abnormally high or graded value post-baseline, both abnormalities are shown in the tables. (This means that the sum of the percentages can be more than 100%)

An abnormality will be considered treatment-emergent in a particular phase if it is worse than baseline. If baseline is missing, the abnormality is always considered as treatment-emergent. A

shift from ‘abnormally low’ at baseline to ‘abnormally high’ or ‘grade ...’ post baseline (or vice versa) is also treatment-emergent.

Analysis Methods

Actual values and change from baseline will be summarized by treatment group at each scheduled time point. The number and percentage of will be shown in a cross-tabulation of the toxicity/abnormality post-baseline versus baseline at each scheduled time point.

Additionally, a cross-tabulation of the worst toxicity/abnormality versus baseline will be presented per phase (Treatment phase, Follow-up phase) and for the combination of Treatment and follow-up phase. This table will also show the number and percentage of subjects per worst toxicity/abnormality, the number and percentage of subjects per treatment-emergent worst toxicity/abnormality and the cumulative number of subjects per treatment-emergent toxicity/abnormality or worse.

Mean±SE graphs over time for the actual values and changes from reference will be generated for all tests performed.

A tabulation of the worst QT/QTc change versus baseline per treatment per phase will be presented

A listing of abnormal individual subject VS values will be provided.

4.4. VIROLOGY

The emergence of viral resistance will be evaluated by sequencing the RSV polymerase L-gene and other regions (only if no mutations are seen in the L-gene) and looking for changes from baseline, defined as before first dose of ALS-008176. All baseline subject samples will be sequenced to identify pre-existing mutations in their L gene. All post-baseline subject samples that show no viral suppression or viral rebound will be sequenced to identify mutations in the L gene that have occurred after the start of treatment with ALS-008176. Ultra deep sequencing will be used to sequence the L gene for all the subjects. A cut-off of 10-15% will be used to analyze the results. The analysis of the viral resistance data will be documented in a separate clinical virology report.

4.4.1. Analysis Time Points

Virology result will be assigned to the visit windows as described in section 2.1. In addition, the below time points will be considered:

- Baseline (BL): Last available pre-dose time point in the study with sequencing data available
- Time Point of Sequence at End of Treatment (EOTSTPT): Last available post-baseline time point during the treatment phase with sequencing data available
- Time Point of Sequence at End of Study (EOSSTPT): Last available post-baseline time point in the study with sequencing data available
- Entire post-baseline phase: Aggregate of all available post-baseline time points in the study with sequencing data available

4.4.2. Virus Strain Typing

RSV will be classified into virus strain subtypes based on a duplex qRT-PCR assay.

4.4.2.1. Analysis Methods

The analysis RSV Subtype at baseline will be tabulated and used in the subgroup analyses.

4.4.3. Viral Sequencing

Sequencing of the entire L-gene will be performed to identify pre-existing and/or emerging genetic variations. The frequency of these genetic variations as well as the effect of pre-existing genetic variations on treatment outcome will be explored.

Definitions

Genetic variations are defined as changes (on amino acid or nucleotide level) in the subject's virus's sequence compared to a reference sequence. Genetic variations can include substitutions, insertions and deletions. The reference sequence to be used is a sequence of the L gene of a wild

type strain such as A2 or Long strains in case of comparison to a baseline sample or the baseline sample if wild type when comparing to post-baseline sample.

- **Wild type:** If – at certain position – the amino acid/nucleotide in the subject’s virus’s sequence matches the reference sequence, that is no genetic variation is present at that position, the virus is considered to be wild type at that position.
- **Emerging genetic variation:** If – at certain position - a genetic variation is absent at Baseline but present at a later time point, the genetic variation considered to be emerging at that time point.
- **Genetic variation profile:** a specific genetic variation or combination of genetic variations at one or more time points

When analyzing the pre-existing and/or emerging genetic variations, special attention will be paid to the following (combination of) genetic variations: M628L, A789V, L795I, I796V.

Parameters to analyze

- Number (%) of subjects with a genetic variations at a specific position.
- Number (%) of subjects with a specific genetic variation.
- Number (%) of subjects with a specific genetic variation profile.
- Number (%) of subjects with a number of genetic variations in a specific genetic area of interest.

The following rules will be taken into account to count the number of genetic variations at a specific time point:

- If, at the selected time point, different genetic variations occur/emerge at the same position, this will be counted only once.
- Wild type is never counted as a genetic variation.
- Insertions and deletions will be counted as a separate genetic variations, even if at the same position a genetic variation is already present.
- Subjects with viral sequencing data at the selected time point, but without (emerging) genetic variations of a specific list, should be classified as having zero (emerging) genetic variations for that list.

The focus will be on genetic variations at selected time points, emerging genetic variations and reversion to wild type or baseline state.

4.4.3.1. Analysis Methods

Frequencies and percentages will be presented at the time points specified above for the specified parameters. The denominator is the number of subjects with viral sequencing data, within the region, at the selected time point(s). Results will be shown by time point and region.

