9.2. Efficacy Evaluations

Viral Load Determination

As an evaluation of antiviral activity of ALS-008176, RSV RNA viral load will be measured in mid-turbinate nasal swabs (obtained from non-intubated subjects) or in mid-turbinate nasal swabs and endotracheal samples (obtained from intubated subjects or via suction through tracheostomy or other sampling methods) using qRT-PCR performed at the central laboratory. Samples for the determination of RSV viral load will be taken as specified in the [Time and Events Schedule](#) and Section [9.1.3](#).

RSV infectious viral load may be measured in mid-turbinate nasal swabs (if non-intubated) or in mid-turbinate nasal swabs and endotracheal samples (if intubated) using a quantitative culture method (plaque assay) in a selected number of subjects and samples at the sponsor's discretion.

Changes in viral load will be evaluated but will not be regarded as AEs or SAEs.

Viral L-gene Sequencing for Viral Resistance

Viral sequencing analysis will be performed by sequencing the polymerase L-gene and other regions of the RSV genome (may be performed if no mutations are seen in the L-gene) in samples taken before treatment (at baseline), during treatment, and posttreatment, to identify preexisting sequence polymorphisms and to characterize emerging RSV variants.

The L-gene will be sequenced pretreatment in all subjects and postbaseline in subjects not achieving viral suppression. The sequencing of postbaseline samples may be triggered at the discretion of the sponsor's virologist, based on the changes in RSV RNA viral load observed in each individual subject and the limits of the sequencing assay. The impact of newly identified mutations on in vitro antiviral activity of ALS-008176 or other RSV molecules may be assessed in in vitro studies.

Other regions of the RSV genome may also be sequenced at the sponsor's discretion.

Changes in the viral sequence will be evaluated but will not be regarded as AEs or SAEs.

Clinical Course of RSV Infection

The study will include the following evaluations of the clinical course of RSV infection:

- Clinical evaluation including, but not limited to:
 - Oxygen requirement type (eg, supplemental oxygen, noninvasive positive pressure ventilation, endotracheal-mechanical ventilation, mechanical ventilation by tracheostomy), duration, and amount.
 - Body weight.

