2.4. Statistical Methods

This SAP covers the statistical analysis for the final analysis. The interim analysis and IDMC analysis will be described in separate SAPs. Details of the single displays are described in the Data Presentation Specifications (DPS).

- The analysis population will be indicated in the titles of the displays.
- Unless stated otherwise, all results will be presented per treatment group. Tables on subject disposition, exposure, demographic data and baseline disease characteristics will include a ‘Total’ group, pooling all subjects. Tables on safety will include a “ALS-008176” group.
- Listings will be presented by treatment group and ordered by subject number and time point (if applicable).
- All outputs should be self-explanatory and therefore appropriate footnotes will be provided to clarify the contents of each listing, table or graph.
- In case the X-axis of a graph shows a time component, the distances between the time points will be proportional (not equidistant). Furthermore, when statistics are joined over time by a line, the actual statistics will be depicted by means of a symbol.
- Unless specified otherwise, continuous parameters will be summarized using the following statistics: number of observations, mean, standard deviation, minimum, median and maximum. The mean and median will be presented with one decimal place, while the standard deviation with two decimal places more than the decimal places of the raw data. The minimum and maximum will be presented to the same number of decimal places as the raw data.
- RSV RNA viral load mentioned in this document refers to the RSV RNA viral load qRT-PCR from nasal swab, unless otherwise stated.

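### Post-baseline resistance percentages are conditional on being sequenced, which depends on virologic outcome, and no ITT-i percentage is planned beside them

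*SAP*

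**What the plan says.** **Who is sequenced.** Protocol 9.2 states: "The L-gene will be sequenced pretreatment in all subjects and postbaseline in subjects not achieving viral suppression". It adds a discretionary element, "The sequencing of postbaseline samples may be triggered at the discretion of the sponsor's virologist", guided by each subject's viral load changes and by what the assay can sequence. SAP 4.4 sequences all baseline samples and then gives its post-baseline rule: "All post-baseline subject samples that show no viral suppression or viral rebound will be sequenced". The sentence after that says ultra-deep sequencing of the L gene applies to every subject.

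**What is counted.** SAP 4.4.3 calls a variation emerging when "a genetic variation is absent at Baseline but present at a later time point", so a subject needs a post-baseline sequence to be a case. The reported parameters take the form "Number (%) of subjects with a specific genetic variation". A subject is classed as having zero emerging variations only if sequencing data exist at that time point.

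**What it is divided by.** SAP 4.4.3.1 states: "The denominator is the number of subjects with viral sequencing data, within the region, at the selected time point(s"). SAP 4.4.1 defines EOTSTPT, EOSSTPT and the entire post-baseline phase by the availability of such data.

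**How it is shown.** SAP 4.4.3.1 mentions display by time point and region. Display by arm follows from the general rule in SAP 2.4: "Unless stated otherwise, all results will be presented per treatment group". No test of the sequencing results is planned.

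**What it serves.** Emergence of resistant virus is a secondary objective in both documents, and post-baseline sequence change is a secondary endpoint in Protocol 2.1.2. Protocol 11 assigns the ITT infected population to efficacy and virologic analyses alike.

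**The concern.** A subject whose virus is suppressed, and who is therefore not sequenced after baseline, is in neither the numerator nor the denominator. Entry to the denominator depends on suppression, which an antiviral is meant to change. If the drug works, fewer active than placebo subjects may be sequenced. The same number of cases would then show as a larger percentage on active treatment. A reader of a by-arm table would naturally take these percentages as the chance that a treated patient develops a variation, and they do not estimate that. The plan provides no ITT-i percentage to set beside them and does not require the reasons for non-sequencing to be reported.

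**Working it through.** The plan states no resistance rate, sequenced fraction or precision for this analysis, so there is no figure of its own to reproduce.

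**Inputs from the documents.** 30 subjects per arm (SAP 1.2). SAP 4.2.3.2 takes 90 as the expected ITT-i size, so 30 also serves as the ITT-i number per arm. The denominator is subjects with sequencing data (SAP 4.4.3.1).

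**Assumed inputs.** The share sequenced after baseline, *f*, from 20% to 80%. Two subjects with emergence in each arm, all among those sequenced. All 30 have a baseline sequence.

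**Formula.** Let p_seq and p_un be the emergence proportions in sequenced and unsequenced subjects, and r = p_un/p_seq. Then

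p_all = f × p_seq + (1 − f) × p_un, so p_seq/p_all = 1/[f + (1 − f) × r].

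**Ratio of the SAP percentage to the ITT-i risk:**

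| f | r = 0 | r = 0.5 | r = 1 | r = 1.5 |
|---|---|---|---|---|
| 0.8 | 1.25 | 1.11 | 1.00 | 0.91 |
| 0.6 | 1.67 | 1.25 | 1.00 | 0.83 |
| 0.4 | 2.50 | 1.43 | 1.00 | 0.77 |
| 0.2 | 5.00 | 1.67 | 1.00 | 0.71 |

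At r = 0 the ratio is 1/f, that is ITT-i/sequenced. This is the most the percentage can be inflated. At r = 1 there is no distortion, and above 1 the SAP percentage understates the risk.

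**By-arm illustration.** True emergence is the same in both arms, 2/30 = 6.7%, with r = 0:

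| Sequenced, placebo vs active | SAP percentage, placebo | SAP percentage, active |
|---|---|---|
| 24 vs 18 | 2/24 = 8.3% | 2/18 = 11.1% |
| 24 vs 12 | 2/24 = 8.3% | 2/12 = 16.7% |
| 18 vs 6 | 2/18 = 11.1% | 2/6 = 33.3% |

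In each row the whole arm difference comes from the denominator.

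**How strong the selection is.** The two rules are written at different levels. Protocol 9.2 selects subjects who do not achieve suppression. SAP 4.4 selects samples. Swabs are daily to Day 7, then on Days 10, 14 and 28. On the sample-level reading, one early unsuppressed swab could be enough to bring a subject into the denominator for the entire post-baseline phase. In that case *f* could approach 1 and the ratio would approach 1. On the subject-level reading, *f* could be much lower. The documents do not define suppression or rebound, so they do not settle which reading applies.

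**The case against.** The strongest case against runs as follows. This is a descriptive table outside the primary endpoint and alpha control, with no test or risk difference. Counts accompany the percentages, so a reader can divide by the ITT-i number. A sequenced denominator is natural for describing variation among sequenced virus, position by position. Resistance is also to be covered in a separate clinical virology report that is not available here. The SAP sentence about sequencing every subject might remove the selection altogether.

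Much of this limits the point without removing it. Readers can re-divide the counts, but the plan does not ask for the ITT-i figure or for the reasons why subjects were not sequenced. The sentence about every subject directly follows the selective rule and reads as naming the method. If it means more than that, it contradicts the selective rule and must be reconciled with it.

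Three stronger readings are tempting, and the documents do not support them:

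- **That emergence is necessarily overstated by treated/sequenced.** This holds only at r = 0. Lower emergence in unsequenced subjects is plausible when selection is on failed suppression, but it is not established.
- **That the sequenced fraction will differ by arm.** This is expected only if the drug suppresses virus. Protocol 1.1 says efficacy in natural infection is not yet shown.
- **That an ITT-i figure with every unsequenced subject scored negative should replace the planned one.** Protocol 9.2 lets assay limits and the virologist's judgement decide who is sequenced, so a missing sequence is partly missing data. Scoring it as negative can understate emergence, and unequally by arm.

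**Conclusion.** The concern holds in a limited form. The post-baseline percentages in SAP 4.4.3.1 are conditional on an outcome that arises after randomization, and they cannot be read or compared across arms as a risk per ITT-i subject. That much follows from the text, apart from the one sentence on sequencing every subject, taken here as naming the method.

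The direction is overstatement if r < 1, with ITT-i/sequenced as the ceiling. The size cannot be computed from the documents; the 8.3% against 16.7% example rests wholly on assumed counts. Baseline percentages are not affected. The SAP counts genetic variations, not confirmed resistance, and makes no inferential comparison. A change is still worth making, because these percentages are the planned summary for a secondary objective and the remedy is cheap.

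**What to change.** In SAP 4.4.3.1, for emerging variations at EOTSTPT, EOSSTPT and the entire post-baseline phase:

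1. Add, by treatment arm, the count and percentage over all ITT-i subjects with baseline sequencing data, labelled 'emerging variation detected' and footnoted as a lower bound.
2. Show beside it the number sequenced after baseline, and the number not sequenced by reason: suppressed, assay limit, no sample, not triggered.
3. Keep the existing percentage, labelled as conditional on being sequenced.
4. Reconcile the subject-level rule in Protocol 9.2 with the sample-level rule in SAP 4.4 and with the SAP sentence on sequencing every subject.

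The cost is SAP wording and an added row or column in the tables. No new samples are needed, though the reason for not sequencing has to be recorded. The drawback is that the ITT-i figure misses any variation carried by unsequenced virus, so it should not appear without the number sequenced.

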4.5. MEDICAL RESOURCE UTILIZATION

Medical resource utilization will be summarized descriptively (number and percentage of subjects) by treatment group at each scheduled time point.

4.6. OTHERS

Relationship between RSV RNA viral load and RSV viral load by qRT-PCR (intubated subjects)

To make a comparison of the RSV RNA viral loads measured in mid-turbinate nasal swabs and endotracheal samples from intubated subjects, scatter plots will be created plotting the RSV RNA viral loads versus the RSV viral load as measured by qRT-PCR of endotracheal samples.

Relationship between viral kinetics and clinical outcome

Kaplan-Meier analysis by quartiles of viral load $AUC_{0-7 \text{ days}}$ for:

- The Length of Hospital Stay/Need (both since treatment initiation and since hospital admission)
- Time to return to pre-RSV functional status (KATZ ADL score)
- Time to clinical stability

A summary table including number of subjects included in the analysis, number of subjects censored, 25th and 75th percentiles and median with 95% confidence intervals based on log-log transformation method, will be presented by quartiles of viral load $AUC_{0-7 \text{ days}}$ parameter.

A Tabulation of the need for additional oxygen supplementation will be presented by quartiles of viral load $AUC_{0-7 \text{ days}}$.

Evolution of diffusing capacity

To explore the evolution of diffusing capacity of the lung for carbon monoxide (DLCO) and spirometry in subjects hospitalized due to RSV infection, descriptive statistics and mean (SE) plots will be shown and the changes from baseline calculated by treatment group.

Impact of ALS-008176 on the infectious viral load

The impact of ALS-008176 on the infectious viral load will be evaluated by descriptive statistics on the RSV infectious viral load as measured using quantitative viral culture (plaque assay).

ATTACHMENT

DMID ADULT TOXICITY GRADES FOR LABORATORY PARAMETERS

PARAMETER	Unit	GRADE 1	GRADE 2	GRADE 3	GRADE 4
Hemoglobin	g/dL	10.5 – 9.5	<9.5 – 8.0	<8.0 – 6.5	<6.5
Absolute Neutrophil Count	GIGA/L	1.50 – 1.00	<1.00 – 0.75	<0.75 – 0.50	<0.50
Platelets	GIGA/L	<100 – 75	<75 – 50	<50 – 20	<20
WBC, high	GIGA/L	11 – <13	13 – <15	15 – 30	>30
WBC, low	GIGA/L	1 – <4			<1
Fibrinogen, high	mg/dL	400 – 600	>600		
	µmol/L	11.76 – 17.65	>17.65		
Fibrinogen, low	mg/dL	200 – 100	<100 – 50	<50	
	µmol/L	5.88 – 2.94	<2.94 – 1.47	<1.47	
Prothrombin Time		>1.00 x ULN – 1.25 x ULN	>1.25 x ULN – 1.50 x ULN	>1.50 x ULN – 3.00 x ULN	>3.00 x ULN
Activated Partial Thromboplastin Time		>1.00 x ULN – 1.66 x ULN	>1.66 x ULN – 2.33 x ULN	>2.33 x ULN – 3.00 x ULN	>3.00 x ULN
AST		>1.0 x ULN – <2.0 x ULN	2.0 x ULN – <3.0 x ULN	3.0 x ULN – 8.0 x ULN	>8.0 x ULN
ALT		>1.0 x ULN – <2.0 x ULN	2.0 x ULN – <3.0 x ULN	3.0 x ULN – 8.0 x ULN	>8.0 x ULN
GGT		>1.0 x ULN – <2.0 x ULN	2.0 x ULN – <3.0 x ULN	3.0 x ULN – 8.0 x ULN	>8.0 x ULN
Alkaline Phosphatase		>1.0 x ULN – <2.0 x ULN	2.0 x ULN – <3.0 x ULN	3.0 x ULN – 8.0 x ULN	>8.0 x ULN
Amylase		>1.0 x ULN – 1.5 x ULN	>1.5 x ULN – 2.0 x ULN	>2.0 x ULN – 5.0 x ULN	>5.0 x ULN
Lipase		>1.0 x ULN – 1.5 x ULN	>1.5 x ULN – 2.0 x ULN	>2.0 x ULN – 5.0 x ULN	>5.0 x ULN
Hyponatremia	mEq/L mmol/L	135 – 130	<130 – 123	<123 – 116	<116
Hypernatremia	mEq/L mmol/L	146 – 150	>150 – 157	>157 – 165	>165
Hypokalemia	mEq/L mmol/L	3.4 – 3.0	<3.0 – 2.5	<2.5 – 2.0	<2.0
Hyperkalemia	mEq/L mmol/L	5.6 – 6.0	>6.0 – 6.5	>6.5 – 7.0	>7.0
Hypoalbuminemia	g/dL	<LLN – 3	<3 – 2	<2	
Hypoglycemia	mg/dL	64 – 55	<55 – 40	<40 – 30	<30
	mmol/L	3.55 – 3.05	<3.05 – 2.22	<2.22 – 1.67	<1.67
Hyperglycemia	mg/dL	116 – 160	>160 – 250	>250 – 500	>500
	mmol/L	6.44 – 8.88	>8.88 – 13.88	>13.88 – 27.75	>27.75
Hypocalcemia (corr. for albumin)	mg/dL	8.4 – 7.8	<7.8 – 7.0	<7.0 – 6.1	<6.1
	mmol/L	2.10 – 1.95	<1.95 – 1.75	<1.75 – 1.52	<1.52
Hypercalcemia (corr. for albumin)	mg/dL	10.6 – 11.5	>11.5 – 12.5	>12.5 – 13.5	>13.5
	mmol/L	2.64 – 2.87	>2.87 – 3.12	>3.12 – 3.37	>3.37
Hypomagnesemia	mEq/L	1.4 – 1.2	<1.2 – 0.9	<0.9 – 0.6	<0.6
	mmol/L	0.70 – 0.60	<0.60 – 0.45	<0.45 – 0.30	<0.30
Hypophosphatemia	mg/dL	2.4 – 2.0	<2.0 – 1.5	<1.5 – 1.0	<1.0
	mmol/L	0.77 – 0.65	<0.65 – 0.48	<0.48 – 0.32	<0.32
Hyperbilirubinemia (TB)		>1.0 x ULN – <1.5 x ULN	1.5 x ULN – <2.0 x ULN	2.0 x ULN – 3.0 x ULN	>3.0 x ULN

PARAMETER	Unit	GRADE 1	GRADE 2	GRADE 3	GRADE 4
